### 2.4.2 Rationale for Exploratory Correlative Studies

Exploratory correlative studies will be performed to evaluate immune system activation and for potential biomarker identification. The specific studies proposed include: 1) assessment of immune cell composition by IHC, gene expression profiling and cytokine production within the TME; 2) whole genome or exome sequencing to assess mutational load and potentially identify predictors of response or resistance; 3) plasma-based markers to correlate with response.

Paired pre-treatment and on treatment core biopsies will be mandatory for patients on the part 2 of this study and optional for patients on part 1. Biopsies at time of progression will be optional. Blood samples will be collected prior to treatment and during treatment as described in the study calendar.

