### **3. PATIENT SELECTION**

#### **3.1 Eligibility Criteria**

- 3.1.1 Subjects with histologically confirmed advanced, progressive, well-differentiated nonfunctional NET of the pancreas, lung or gastrointestinal (GI) tract per the 8th International Association for the Study of Lung Cancer classification (IASLC) or the American Joint Committee on Cancer (AJCC) Staging Handbook, 7th edition. Progression must be documented over the prior 12 months.
- 3.1.2 Measurable disease by CT or MRI per RECIST 1.1 criteria (Appendix 3); radiographic tumor assessment performed within 28 days before treatment. Target lesions may be located in a previously irradiated field if there is documented (radiographic) disease progression in that site after the completion of radiation therapy.
- 3.1.3 Prior therapy, including everolimus, octreotide, surgery, chemoradiation, is all permitted after being properly noted. This prior therapy must have been completed at least 28 days prior to study enrollment.
- 3.1.4 Patients with lung NETs must have progressed after at least 1 line of therapy. Patients with GI NETs must have had at least 2 lines of prior therapy.
- 3.1.5 Subjects are to have tumor tissue sample available at central lab for PD -L1 IHC testing during the screening period. Subjects can initiate therapy before the result of IHC testing.
- 3.1.6 (Stage 2 only) Subjects must be willing to undergo 2 sets of core needle biopsies (pre-treatment and at 6-8 weeks on therapy) if there are lesions amenable to biopsy. Subjects without a lesion amendable to biopsy will still be permitted to enroll provided they have an archival tumor sample for PD-L1 IHC testing. An optional core biopsy will be requested at progression.

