## 6. ADVERSE EVENTS: LIST AND REPORTING REQUIREMENTS

This study will use the descriptions and grading scales found in the revised National Cancer Institute Common Terminology Criteria for Adverse Events (CTCAE) Version 4.0 for adverse event reporting that can be found at [http://ctep.cancer.gov/protocolDevelopment/electronic\\_applications/ctc.htm](http://ctep.cancer.gov/protocolDevelopment/electronic_applications/ctc.htm).

Information about all AEs, whether volunteered by the subject, discovered by investigator questioning, or detected through physical examination, laboratory test or other means, will be collected, recorded, and followed as appropriate.

All AEs and SAEs experienced by subjects will be collected and reported from the first dose of nivolumab, throughout the study, and will only be followed for 4 weeks unless related to the investigational agent. All SAEs will be collected for 100 days after the last dose of nivolumab. Subjects who have an ongoing AE related to the study procedures and/or medication(s) may continue to be periodically contacted by a member of the study staff until the event is resolved or determined to be irreversible by the investigator.

**Laboratory abnormalities:** Laboratory abnormalities present at the screening visit will be recorded as pre-treatment signs and symptoms. After study treatment administration, all grade 3 and 4 clinical laboratory results that represent an increase in severity from baseline will be reported as adverse events. A grade 1 or 2 clinical laboratory abnormality should be

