## 6.1 Definitions

### 6.1.1 Adverse Event

An adverse event (AE) is defined as any new untoward medical occurrence or worsening of a preexisting medical condition in a clinical investigation subject administered study drug and that does not necessarily have a causal relationship with this treatment. An AE can therefore be any unfavorable and unintended sign (such as an abnormal laboratory finding), symptom, or disease temporally associated with the use of study drug, whether or not considered related to the study drug.

BMS will be reporting adverse events to regulatory authorities and ethics committees according to local applicable laws including European Directive 2001/20/EC and FDA Code of Federal Regulations 21 CFR Parts 312 and 320.

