#### 8.1.1 Tumor Tissue Handling

A formalin-fixed, paraffin-embedded (FFPE) tumor tissue block (preferred) or 10 unstained slides of tumor sample (archival or recent) for biomarker evaluation must be available and submitted for correlative studies in order for a subject to be enrolled as described in the **Laboratory Manual**. If fewer than 10 slides are available, the Principal Investigator may still approve enrollment of subjects upon review of the case. Excisional, incisional or core needle biopsies are strongly preferred, however samples collected via endobronchial ultrasound (EBUS) guided biopsy (using a 22g needle or larger) and transbronchial lung biopsy (TBLB) are acceptable. In certain cases, the Principal Investigator may approve submission of samples collected via other methods.

If a new biopsy is taken (i.e. no archival tissue is available), up to 5 core biopsies are recommended at baseline. Otherwise, up to 4 core biopsies should be collected at baseline and at other time points per the Study Calendar. An assessment of biopsy quality by a pathologist is encouraged at the time of the procedure. The tumor tissue that is obtained from these biopsies will be allocated to FFPE, fresh frozen and for RNA later as described in the **Laboratory Manual**. The investigator, in consultation with the radiology staff, must determine the degree of risk associated with the procedure and find it acceptable. Biopsies may be done with local anesthesia or conscious sedation. Institutional guidelines for the safe performance of biopsies should be followed. Excisional biopsies may be performed to obtain tumor biopsy samples. Invasive procedures that require general anesthesia should not be performed to obtain a biopsy specimen. However, if a surgical procedure is performed for a clinical indication, excess tumor tissue may be used for research purposes with the consent of the subject.

A pathology report should be provided with tumor samples.

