	
a: LDH, AST, ALT, ALP, T. bili, BUN or serum urea level, creatinine, albumin, Ca, Mg, Na, K, Cl, phosphate, glucose, amylase, lipase, TSH, Free T4, Free T3, within 14 days prior to first dose.
 
b: Hep B/C (HBV sAg, HCV antibody or HCV RNA), within 28 days prior to first dose.
 
c: Thyroid Function Testing to be evaluated every 6 weeks
 
d: A serum or urine pregnancy testing is required prior to study enrollment/registration, also within 24 hours prior to D1 (and extension to 72 hours may be granted if unable to obtain within 24 hrs). Must be reassessed every 4 weeks.
 
e: CT scan of the chest and other relevant sites as well as MRI brain with gadolinium (or CT scan brain with contrast if MRI is contraindicated) will be performed <math>\leq</math> 4 weeks prior to the start of therapy. For subsequent scans, may be done within +/- 7 days of intended visit.
 
f: Within 72 hrs prior to dosing to include CBC w/ differential, AST, ALT, ALP, T. bili, BUN or serum urea level, creatinine, albumin, Ca, Mg, Na, K, Cl, LDH, phosphate, glucose, amylase, lipase, TSH (with reflexive Free T4 and Free T3). Note: C1D1 labs do not need to be repeated if they were performed within 14 days of dosing.
 
g: All treatments may be performed +/- 2 days of the intended treatment administration dates schedule for all cycles.
 
h: Recent sample or archival obtained. One (1) formalin-fixed paraffin embedded tumor tissue block or a minimum of 10 unstained tumor tissue sections are acceptable.
 
i: Mandatory fresh tissue will be collected for biomarker studies at baseline and on treatment (week 6-8) for patients enrolled in the second stage of the study.
 
j: Immunogenecity samples should be collected just before the administration of the first drug (preferably within 30 minutes).
 
k: Adverse event evaluation as per Common Terminology Criteria for Adverse Events (CTCAE) version 4.0
 
l: Survival follow-up may be done via phone call for survival status and subsequent therapy
 
m: CT if the subject came off study for reasons other than PD
 
n: EOT assessments do not need to be repeated if performed within 14 days
 
o: In order to minimize the need for research-only in-person visits, telemedicine visits may be substituted for in-person clinical trial visits or portions of clinical trial visits where determined to be appropriate and where determined by the investigator not to increase the participant's risks. Prior to initiating telemedicine for study visits the study team will explain to the participant, what a telemedicine visit entails and confirm that the study participant is in agreement and able to proceed with this method. Telemedicine acknowledgement will be obtained in accordance with the Guidance for Use of Telemedicine in Research. In the event telemedicine is not deemed feasible, the study visit will proceed as an in-person visit. Telemedicine visits will be conducted using HIPAA compliant method approved by the Health System and within licensing restrictions.
								

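### AE and SAE collection opens at the first nivolumab dose, so complications of the stage 2 pre-treatment research biopsy fall outside required safety reporting, and other sections conflict on this

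*Combined protocol and SAP*

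**What the plan says.** **Start of collection.** Section 6 sets a single start for safety data: "All AEs and SAEs experienced by subjects will be collected and reported from the first dose of nivolumab". It makes no exception for study procedures. Section 6.1.1 defines an AE as a new occurrence or worsening "in a clinical investigation subject administered study drug". Section 6.1.2 ties an SAE to an occurrence at any dose.

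**The biopsy.** Section 2.4.2 says: "Paired pre-treatment and on treatment core biopsies will be mandatory for patients on the part 2 of this study". Section 9 (Study Calendar, footnote i) also calls the stage 2 baseline tissue mandatory, and the calendar places it in the screening column, 0 to 28 days before dosing. Section 3.1.6 adds a condition: "Subjects without a lesion amendable to biopsy will still be permitted to enroll provided they have an archival tumor sample". Section 8.1.1 gives the number of cores: "Otherwise, up to 4 core biopsies should be collected at baseline and at other time points per the Study Calendar", or up to 5 where there is no archival tissue. The same section recognises that the procedure carries risk: the investigator "must determine the degree of risk associated with the procedure and find it acceptable". It says nothing about reporting complications.

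**Analysis.** Section 12.4.3 carries out the safety analysis in treated subjects. Section 12.3.1 defines these as subjects who have had a full dose of each drug at least once.

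**The concern.** The pre-treatment biopsy is an invasive procedure required for biomarker research, and it comes before the only stated opening of the reporting window. Followed as written, Section 6 does not require a bleed or pneumothorax from it to be recorded or sent on as an AE or SAE. The bodies that oversee the trial need such events to judge whether the biopsy requirement remains acceptable. Section 10.1 has the DSMB review toxicity at least annually, but nothing in the plan ensures that pre-dose biopsy harm is in the data it receives. The least visible case is a subject whose complication prevents dosing: the event precedes the window, and the subject is not in the safety population.

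**Working it through.** The main check compares texts; arithmetic enters only for the size.

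**Step 1: the same event at the two biopsies.**

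| | Baseline biopsy | Week 6-8 biopsy |
|---|---|---|
| Timing (Section 9) | Screening, before first dose | On treatment |
| Inside the Section 6 window? | No | Yes |
| Subject already given study drug (6.1.1)? | No | Yes |
| Must be collected as AE/SAE under these two sections? | No | Yes |
| In the treated safety set (12.3.1, 12.4.3)? | Only if both drugs are later given | Yes, if a full dose of each drug was given |

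**Step 2: does other text set an earlier start?**
- Section 6, ongoing procedure-related AEs: allows continued contact with the subject. It shows that such events were foreseen, but opens no pre-dose window.
- Section 6, screening laboratory abnormalities: recorded as pre-treatment signs and symptoms, not as AEs.
- Section 6.2: assesses relationship to study drug only.
- Section 6.4: a procedure-associated SAE may be reported if it could modify study conduct.
- Section 6.5.1: SAE notification whatever the cause, for the course of the investigation. It gives no start date.
- Section 6.5.5: IRB reporting is tied to events related to the investigational product.
- Section 9: the Symptom/Toxicity row is marked at screening. Its letter, j, points to an immunogenicity-sample note. Footnote k, on AE evaluation, is attached to no row. Neither says that a pre-dose finding is reportable.

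No section starts collection at consent or at the first study procedure.

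**Step 3: size.** Inputs from Section 12.2: 20 subjects in stage 1, 56 in total, stop if 1 or fewer respond, response rates 0.05 and 0.15, 15% screening failure.

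- Check on the design: the probability of early termination at 0.05 is 0.95^20 + 20 × 0.05 × 0.95^19 = 0.736, and the expected sample size is 20 + (1 - 0.7358) × 36 = 29.51. Both match the plan. The exact two-stage calculation also reproduces the error rates (0.097 and 0.199).
- Treated stage 2 subjects: 56 - 20 = 36, or 36/56 = 64% of the total.
- Chance that stage 2 opens: 1 - 0.736 = 0.264 at a response rate of 0.05, and 1 - 0.176 = 0.824 at 0.15.
- With stage 2 screen failures, assuming the 15% applies equally to stage 2: 36/0.85 = 42.4, so up to 43. The plan's 64 corresponds to 56 × 1.15 = 64.4; the same method gives 36 × 1.15 = 41.4.

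**Step 4: illustration.** The documents give no biopsy complication rate. For an assumed serious-complication rate q, the expected number of events in 36 subjects is 36q, and the chance of at least one is 1 - (1 - q)^36.

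| Assumed q | Expected events | Chance of at least one |
|---|---|---|
| 0.5% | 0.18 | 17% |
| 1% | 0.36 | 30% |
| 2% | 0.72 | 52% |
| 3% | 1.08 | 67% |
| 5% | 1.80 | 84% |

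These figures are conditional on stage 2 opening and on all 36 being biopsied before dosing.

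**The case against.** The strongest counter-text is Section 6.5.1. It requires SAEs to reach the principal investigator within 24 hours regardless of causality, and requires notice to the monitoring committee and the IRB of SAEs from any cause during the investigation, with no first-dose limit. Sections 10.2 and 10.3 add safety meetings at least monthly and review of safety outcomes by the principal investigator. If the calendar lettering is a slip, footnote k would schedule an AE evaluation at screening.

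This has force. A reader might infer that biopsy complications are neither counted nor sent to the IRB or DSMB. The documents do not support that: a site could reasonably report such an SAE under Section 6.5.1, and the screening assessment could note it. But these sections broaden cause or schedule an assessment; they do not say when reporting starts. Section 6 does, and it says first dose. The result is a conflict, and two sites could act differently.

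A reader might also infer that everyone harmed before dosing is lost from the safety set. That is not so: a subject later given both drugs is in it, although the pre-dose event still lies outside the collection window. Only those never dosed are absent. A treated-subjects set does suit the stated aim of describing the combination's toxicity, so a separate listing is a better remedy than a redefined population.

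Finally, a reader might count 36 of 72 biopsy sets as mandated and pre-dose. Section 3.1.6 requires biopsy only where a lesion is amenable, so both numbers are ceilings.

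The consent pages, Laboratory Manual, institutional biopsy guidelines and DSMB guidance are not available here and may address complications. The protocol's own reporting rule would still need to agree with them.

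**Conclusion.** The point holds as a gap in required reporting, together with a conflict between sections. Under Sections 6 and 6.1.1, a complication of the required stage 2 baseline biopsy need not be collected or reported as an AE or SAE; at week 6-8 it must be. A subject biopsied, harmed and never dosed is also missing from the safety analysis.

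The size is at most 36 treated stage 2 subjects, and only if stage 2 opens, plus any biopsied stage 2 screen failures (a total of about 41 to 43 if the 15% rate applies to stage 2 and all were biopsied before failing). This takes part 2 in Section 2.4.2 to mean stage 2. The event probabilities rest on assumed rates and only show scale.

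The matter concerns participant safety and oversight. It does not touch the response rate, the sample size or the error rates. It should be corrected before stage 2 biopsies begin or continue.

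**What to change.** 1. **Section 6:** collect and report SAEs and study-procedure-related AEs from informed consent, or at least from the first study-specific procedure. Collect other AEs from first dose.
2. **Section 6.1.1:** extend the AE definition to procedure-related events before dosing.
3. **Section 6.2:** add an assessment of relationship to study procedure.
4. **Sections 6.5.1 and 6.5.5:** state the same start date, and make procedure-related SAEs reportable to the IRB.
5. **Section 9:** correct the footnote letter on the Symptom/Toxicity row and say how screening findings are handled.
6. **Section 12.4.3:** add a listing of pre-dose procedure-related events for all consented or biopsied subjects, including those never dosed, with the number biopsied as denominator. Keep the treated set for drug toxicity.

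A change to Section 6 alone would not be enough, because Sections 6.1.1, 6.2 and 6.5.5 would still tie events to study drug. The cost is a few sentences across these sections, an eCRF window change and one listing. No design figure changes.

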## 6.1 Definitions

### 6.1.1 Adverse Event

An adverse event (AE) is defined as any new untoward medical occurrence or worsening of a preexisting medical condition in a clinical investigation subject administered study drug and that does not necessarily have a causal relationship with this treatment. An AE can therefore be any unfavorable and unintended sign (such as an abnormal laboratory finding), symptom, or disease temporally associated with the use of study drug, whether or not considered related to the study drug.

BMS will be reporting adverse events to regulatory authorities and ethics committees according to local applicable laws including European Directive 2001/20/EC and FDA Code of Federal Regulations 21 CFR Parts 312 and 320.

### 6.1.2 Serious Adverse Event

A ***Serious Adverse Event (SAE)*** is any untoward medical occurrence that at any dose:

- results in death
- is life-threatening (defined as an event in which the subject was at risk of death at the time of the event; it does not refer to an event which hypothetically might have caused death if it were more severe)
- requires inpatient hospitalization or causes prolongation of existing hospitalization (see **NOTE** below)
- results in persistent or significant disability/incapacity
- is a congenital anomaly/birth defect
- is an important medical event (defined as a medical event(s) that may not be immediately life-threatening or result in death or hospitalization but, based upon appropriate medical and scientific judgment, may jeopardize the subject or may require intervention [e.g., medical, surgical] to prevent one of the other serious outcomes listed in the definition above.) Examples of such events include, but are not limited to, intensive treatment in an emergency room or at home for allergic bronchospasm; blood dyscrasias or convulsions that do not result in hospitalization.)
- Potential drug induced liver injury (DILI) is also considered an important medical event. (See **Section 6.5.3** for the definition of potential DILI.)
- Suspected transmission of an infectious agent (e.g., pathogenic or nonpathogenic) via the study drug is an SAE.

- Although pregnancy, overdose, cancer, and potential drug induced liver injury (DILI) are not always serious by regulatory definition, these events must be handled as SAEs. (See **Section 6.5.4** for reporting pregnancies).

Any component of a study endpoint that is considered related to study therapy (e.g., death is an endpoint, if death occurred due to anaphylaxis, anaphylaxis must be reported) should be reported as SAE (see **Section 6.5** for reporting details).

**NOTE:** The following hospitalizations are not considered SAEs in BMS clinical studies:

- a visit to the emergency room or other hospital department < 24 hours, that does not result in admission (unless considered an important medical or life-threatening event)
- elective surgery, planned prior to signing consent admissions as per protocol for a planned medical/surgical procedure
- routine health assessment requiring admission for baseline/trending of health status (e.g., routine colonoscopy) medical/surgical admission other than to remedy ill health and planned prior to entry into the study. Appropriate documentation is required in these cases admission encountered for another life circumstance that carries no bearing on health status and requires no medical/surgical intervention (e.g., lack of housing, economic inadequacy, caregiver respite, family circumstances, administrative reason). Admission for administration of anticancer therapy in the absence of any other SAEs

## 6.2 Relationship

The relationship of an AE to the administration of the study drug is to be assessed by the principal investigator according to the following definitions:

- No (unrelated, not related, no relation): The time course between the administration of study drug and the occurrence or worsening of the adverse event rules out a causal relationship and another cause (concomitant drugs, therapies, complications, etc.) is suspected.
- Yes (related): The time course between the administration of study drug and the occurrence or worsening of the adverse event is consistent with a causal relationship and no other cause (concomitant drugs, therapies, complications, etc.) can be identified.

The following factors should also be considered:

- The temporal sequence from study drug administration - The event should occur after the study drug is given. The length of time from study drug exposure to event should be evaluated in the clinical context of the event.
- Underlying, concomitant, intercurrent diseases - Each report should be evaluated in the context of the natural history and course of the disease being treated and any other disease the subject may have.
- Concomitant medication - The other medications the subject is taking or the treatment the subject receives should be examined to determine whether any of them might be recognized to cause the event in question.

- Known response pattern for this class of study drug - Clinical and/or preclinical data may indicate whether a particular response is likely to be a class effect.
- Exposure to physical and/or mental stresses - The exposure to stress might induce adverse changes in the recipient and provide a logical and better explanation for the event.
- The pharmacology and pharmacokinetics of the study drug - The known pharmacologic properties (absorption, distribution, metabolism, and excretion) of the study drug should be considered.

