### 6.4 Handling of Expedited Safety Reports

In accordance with local regulations, BMS and the IND Sponsor will notify investigators of all reported SAEs that are suspected (related to the investigational product) and unexpected (i.e., not previously described in the IB). In the European Union (EU), an event meeting these criteria is termed a Suspected, Unexpected Serious Adverse Reaction (SUSAR). Investigator notification of these events will be in the form of an expedited safety report (ESR).

- Other important findings which may be reported by the as an ESR include: increased frequency of a clinically significant expected SAE, an SAE considered associated with study procedures that could modify the conduct of the study, lack of efficacy that poses significant hazard to study subjects, clinically significant safety finding from a nonclinical (e.g., animal) study, important safety recommendations from a study data monitoring committee, or sponsor decision to end or temporarily halt a clinical study for safety reasons.
- Upon receiving an ESR from BMS, the investigator must review and retain the ESR with the IB. Where required by local regulations or when there is a central IRB/IEC for the study, the sponsor will submit the ESR to the appropriate IRB/IEC. The investigator and IRB/IEC will determine if the informed consent requires revision. The investigator should also comply with the IRB/IEC procedures for reporting any other safety information.
- In addition, suspected serious adverse reactions (whether expected or unexpected) shall be reported by BMS to the relevant competent health authorities in all concerned countries according to local regulations (either as expedited and/or in aggregate reports).

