#### 6.5.3.1 Expedited IND Safety Reports:

**7 Calendar-Day Telephone or Fax Report:** The Sponsor is required to notify the FDA of any fatal or life-threatening adverse event that is unexpected and assessed by the investigator to be possibly related to the investigational agent. Such reports are to be telephoned or faxed [contact]) to the FDA within 7 calendar days of

first learning of the event. Follow-up information will be submitted to the FDA as soon as relevant information is available.

**15 Calendar-Day Written Report:** The Sponsor is required to notify the FDA of any serious adverse event that is unexpected and possibly related to the investigational agent in a written IND Safety Report.

Written IND Safety Reports should include an Analysis of Similar Events in accordance with regulation 21 CFR § 312.32. All safety reports previously filed with the IND concerning similar events should be analyzed. The new report should contain comments on the significance of the new event in light of the previous, similar reports.

Written IND safety reports with Analysis of Similar Events are to be submitted to the FDA within 15 calendar days of first learning of the event. Follow-up information will be submitted to the FDA as soon as relevant information is available.

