#### 12.4.3 Safety Analyses

Safety analysis will be performed in all treated subjects. Descriptive statistics of safety will be presented using National Cancer Institute (NCI) Common Terminology Criteria for Adverse Events (CTCAE) version 4.0. All on-study AEs, drug-related AEs, SAEs and drug-related SAEs, AEs and drug-related AEs leading to drug discontinuation will be tabulated using worst grade per NCI CTCAE v 4.0 criteria by system organ class and preferred term, based on MedDRA terminology. On-study lab parameters including hematology, coagulation, chemistry, liver function and renal function will be summarized using worst grade per NCI CTCAE v 4.0 criteria.

Frequency, management and resolution of IMAEs will be analyzed. A tabular summary of the incidence of overall IMAEs (by preferred term) and serious IMAEs will be performed. A descriptive analysis of IMAEs including time-to-onset, severity, duration, action taken with the study drug, dosing delays of the study drug, corticosteroid details, re-challenge information and outcome of the AE will be individually characterized by IMAE category ([Section 6.6.1](#)).

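### The two causality categories in section 6.2 leave two of four timing-and-cause combinations unclassified, and the safety-reporting triggers do not use the same causality term

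*Combined protocol and SAP*

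**What the plan says.** Section 6.2 has the principal investigator assess relationship under two definitions. For *Yes (related)*, the timing "is consistent with a causal relationship and no other cause (concomitant drugs, therapies, complications, etc.) can be identified". For *No*, the timing "rules out a causal relationship and another cause (concomitant drugs, therapies, complications, etc.) is suspected". A list introduced by "The following factors should also be considered" then names temporal sequence, concurrent disease, concomitant medication, class effects, stress and pharmacology. It gives no default for an event that satisfies neither definition.

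The call is used in the analysis. Section 12.4.3 states: "All on-study AEs, drug-related AEs, SAEs and drug-related SAEs, AEs and drug-related AEs leading to drug discontinuation will be tabulated".

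It is also used in reporting, under varying terms:

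- Section 6.4 notifies investigators of "all reported SAEs that are suspected (related to the investigational product) and unexpected".
- Section 6.5.3.1 (printed after 6.5.6) requires a 7-day FDA report for a fatal or life-threatening event that is "unexpected and assessed by the investigator to be possibly related to the investigational agent". It requires a 15-day report for "any serious adverse event that is unexpected and possibly related to the investigational agent in a written IND Safety Report".
- Section 6.5.1 sends serious, unexpected events to the FDA with no relationship condition.
- Section 6.5.5 ties the IRB report to events that are related.

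**The concern.** A two-level causality scale works only if every event falls on one side or the other. Here the common difficult case does not: an event with plausible timing in a patient whose tumor, infection or other medication could also explain it. The protocol gives reason to expect such events. Section 7.2.9 says that drug-related and unrelated causes of pulmonary findings can be hard to tell apart in lung cancer patients. Section 2.1 lists obstruction, pain, bleeding and pneumonia among the consequences of the tumors themselves. Section 3.1.9 admits patients with liver metastases and raised transaminases.

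Characterizing toxicity is a secondary objective (1.2.1), and there is no control arm. Investigator attribution is therefore the main means of separating drug effect from disease effect. If assessors handle mixed events differently, the drug-related tables have no reproducible definition. The call also decides whether an AE is followed beyond 4 weeks (section 6, opening text), the IRB report under 6.5.5 and the FDA reports under 6.5.3.1.

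**Working it through.** No figure in the plan needs reproducing; the check is on the logic of the definitions and on the terms used.

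**Step 1: cover all cases.** Inputs are the two conditions in section 6.2. Timing is either consistent with the drug or rules it out. Another cause is either present or absent. (The text says *identified* under Yes and *suspected* under No; treating these as the same favors the plan.) Yes = consistent timing AND no other cause. No = timing ruled out AND other cause.

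| Timing | Other cause | Meets Yes? | Meets No? | Result |
|---|---|---|---|---|
| Consistent | None | yes | no | Related |
| Ruled out | Present | no | yes | Unrelated |
| Consistent | Present | no (other cause) | no (timing fits) | No category |
| Ruled out | None | no (timing) | no (no other cause) | No category |

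So 2 of 4 combinations are unclassified. The fourth row is the lesser problem, since most assessors would answer No. The third row is the one that matters.

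**Step 2: look for a tie-break.** The six listed factors help an assessor weigh competing causes. None says which answer to give when timing fits and another cause exists, and no other section supplies a rule.

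**Step 3: follow a mixed event (third row) into the tables of 12.4.3.**

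- Assessor applies Yes literally, so the event is not related: it is missing from the drug-related tables.
- Assessor notes that No also fails and answers Yes: it is included.
- Assessors differ: it depends on who assessed it.

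The direction and size of any distortion depend on this choice, which the text leaves open.

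**Step 4: compare the triggers.**

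| Section | Report | Causality condition | Is it a level in 6.2? |
|---|---|---|---|
| 6.4 | Expedited report to investigators | suspected, glossed as related | only through the gloss |
| 6.5.1 | FDA | none | not needed |
| 6.5.3.1 | FDA, 7 and 15 days | possibly related | no |
| 6.5.5 | IRB | related | yes |

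Two sections set FDA triggers of different width, and the narrower one asks for a level that section 6.2 does not offer.

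**Step 5: list what does not depend on the call.** The all-cause AE and SAE tables (12.4.3); the immune-mediated AE analysis, which counts events whatever their cause (6.6.1); and, under 6.5.1, SAE reporting to the principal investigator within 24 hours and onward notice of SAEs from any cause to the safety committee and IRB.

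**The case against.** The strongest reply is that the gap does little damage. All AEs and SAEs are tabulated whatever their cause, the immune-mediated events are analyzed without a causality test, and section 6.5.1 gives SAEs a causality-free route to the IRB and gives serious, unexpected events one to the FDA. No safety hypothesis or stopping boundary in section 12 uses a drug-related rate, and the response-rate endpoint is untouched. The listed factors also leave room for judgment.

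Most of this stands and limits the harm, but it does not close the gap. Outside endocrine events, the immune-mediated analysis covers only listed categories in which immunosuppressive treatment was given, so it cannot replace the drug-related tables. Judgment without a default is what makes coding vary between assessors. The wider FDA trigger in 6.5.1 conflicts with 6.5.3.1, which is itself a reason to reconcile them.

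A reader might go further and infer that drug-related events will be undercounted, and might put a figure on it. Section 2.3.1 cites a 37% grade 3-4 treatment-related rate in a lung cancer study. If 10% to 30% of those subjects were lost, the rate would become 0.37 × 0.90 = 33% to 0.37 × 0.70 = 26%. The documents do not support this. Mixed events fail No as well as Yes, so the direction is undetermined. The 10% to 30% share is an assumption. The 37% comes from another population and has already passed through an attribution rule that we cannot see. It also counts subjects, and a subject drops out only if every qualifying event has another cause.

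**Conclusion.** The definitional gap is real and can be shown from the text alone: two of four combinations have no category, and nothing elsewhere assigns them. The consequence is inconsistent coding of mixed events, with omission from the drug-related AE, SAE and discontinuation tables if Yes is applied literally. Neither the number of events affected nor the net direction can be derived from the documents.

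The mismatch of reporting terms is also plain. It should not be read as showing that serious events will go unreported, because section 6.5.1 provides routes that do not depend on causality. The point affects the reproducibility of the drug-related safety summaries and the consistency of the reporting rules. It does not affect the primary endpoint or the all-cause safety results.

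**What to change.** In section 6.2, replace the two definitions with an exhaustive pair:

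- *Related*: there is a reasonable possibility that study drug caused or contributed to the event, even if other causes are possible.
- *Not related*: there is no reasonable possibility that it did.

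Keep the list of factors as guidance for that judgment. Use the same term in 6.4, 6.5.3.1 and 6.5.5. Reconcile 6.5.1 with 6.5.3.1 on FDA reports; the IRB routes in 6.5.1 and 6.5.5 should be read together at the same time.

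The drafting cost is two sentences and a few consistent terms. The downside is that somewhat more events will be classed as related. If events have already been assessed under the present wording, they need either reassessment or a note with the tables.

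Sections 5.2 and 5.2.1 use drug-related and treatment-related as conditions for dose delay and discontinuation, so a new definition could change which events meet them. The sponsor must reconcile those passages with section 6.2; no clinical rule is proposed here.
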